### Data Sources

BSWH is the largest not-for-profit integrated healthcare delivery system in Texas and one of the largest in the United States with over 1,000 access points in 46 counties, 49,000 employees, and 7,300 affiliated physicians. This study includes data from 25 hospitals across north and central Texas and 3767 inpatient beds. Data will be obtained from BSWH EHR and laboratory systems. All EHRs are managed on the Epic systems at affiliated hospitals during the study period. Laboratory data systems include SoftLab (SCC) for COVID-19 test results, and SoftBank (SCC) and SafeTrace (Haemonetics) for convalescent plasma data elements. The definition, location and time points of the data elements extracted from Epic are listed in Appendix 4. BSWH will fill this table while implementing data abstraction for transparency and data governance.

All programming scripts used to extract data from the EHRs will be programmed and then validated by a second programmer using a standardized template that requires checking for syntax errors as well as errors in logic. In addition, a random selection of records (n=10–20 records per data point) will be compared and validated against a manual chart review of the data. The programming scripts for each data element will be refined until the match rate with manual extraction is 95%.

Similarly, all programming used to assemble data into an analytic dataset will be programmed and then validated by a second programmer using a standardized template.

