### Study Outcomes

- Safety

Safety events related to plasma transfusion were selected from the Centers for Disease Control and Prevention (CDC) National Healthcare Safety Network (NHSN) Biovigilance Component Hemovigilance Module Surveillance Protocol.a The following safety outcomes will be identified by ICD-10-CM billing codes (Appendix 5).

- Transfusion associated circulatory overload (TACO)
- Transfusion-related acute lung injury (TRALI)
- Anaphylactic reaction

---

a The following events were excluded because they are irrelevant for plasma transfusion or because there are no transfusion-specific billing codes. Transfusion-associated graft vs. host disease (TAGVHD) is associated with a cellular product. Delayed hemolytic transfusion reaction (DHTR) and delayed serologic transfusion reaction (DSTR) are associated with red cells containing products. Post transfusion purpura (PTP) is associated with platelets containing products. No transfusion specific billing codes exist for transfusion-associated dyspnea (TAD) allergic reaction and hypotensive transfusion reaction.

- Febrile non-hemolytic transfusion reaction
- Transfusion-transmitted infection
- Acute hemolytic transfusion reaction
- A composite outcome of thrombotic or thromboembolic complication including stroke, myocardial infarction, venous thromboembolism, deep vein thrombosis, and pulmonary embolism
- A composite outcome of cardiac arrhythmias including ventricular tachycardia, ventricular fibrillation, atrial arrhythmia, and cardiac arrest
- Effectiveness
  - Primary:
    - 28-day in-hospital mortality
  - Secondary:
    - Discharge alive
    - ICU transfer
    - Mechanical ventilation

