## **IV. STATISTICAL ANALYSIS PLAN**

### **All patients**

#### Descriptive Analyses

We will describe distribution of baseline covariates (Appendix 2), including demographics, comorbidities, concomitant medications, and severity measures of COVID-19 for the exposed and unexposed groups. The number of patients, mean, standard deviation, median, interquartile range, and range will be presented for continuous variables, and counts and percentages of patients in each category will be presented for categorical variables.

Given the modest sample size and rarity of the safety outcomes, we will explore the occurrence of safety outcomes, and present counts and percentages.

The crude incidence rates of death in the first 7, 14, 21, and 28 days after the index date will be estimated for the exposed and unexposed groups using the cohort before propensity score matching.

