## V. SAMPLE SIZE

To achieve 80% power for relative risk ratios of at least 0.7 for all-cause mortality, a sample size calculation was performed based on an assumed background survival rate of 0.75 over 28 days among hospitalized COVID-19 patients receiving usual care in the RCT for dexamethasone and a convalescent plasma to comparator ratio of 1:1, 1:2, 1:3 and 1:4. Using a two-sided log-rank test, estimated sample sizes are listed in **Table 1**.

The feasibility assessment found that the maximum number of patients who received convalescent plasma was 729 during April 1, 2020 to August 6, 2020, we greyed out rows in **Table 1** with required sample size surpassing the maximum and deemed those inapplicable.

**Table 1. Sample size estimates given background survival rate of hospitalized COVID-19 patients and 80% of power at a two-sided 0.05 significance level**

Total sample size	Sample size for convalescent plasma	Match ratio	Relative risk ratio
1,000	500	1:1	0.71
1,500	750	1:1	0.76
2,000	1,000	1:1	0.79
2,500	1,250	1:1	0.81
1,000	333	1:2	0.68
1,500	500	1:2	0.74
2,000	666	1:2	0.77
2,500	833	1:2	0.80

Total sample size	Sample size for convalescent plasma	Match ratio	Relative risk ratio
1,000	248	1:3	0.65
1,500	372	1:3	0.71
2,000	496	1:3	0.75
2,500	620	1:3	0.78
1,000	200	1:4	0.61
1,500	300	1:4	0.68
2,000	400	1:4	0.73
2,500	500	1:4	0.76

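### For the rare transfusion-reaction outcomes, the 95% chart-agreement check on 10–20 random records tests almost only agreement on 'no event'

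*Protocol*

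**What the plan says.** The Data Sources section (Protocol, III. Study Design) describes two checks on the extraction scripts. The first is a review of each script by another programmer, who works from a standard template and looks for faults of syntax and of logic. The second is a chart comparison: "a random selection of records (n=10–20 records per data point) will be compared and validated against a manual chart review of the data". The acceptance rule is then: "The programming scripts for each data element will be refined until the match rate with manual extraction is 95" per cent.

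The rule covers every data element. It asks for overall agreement only. It has no separate requirement for records with and without the event, and it does not say whether a new sample is drawn after a script is changed.

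Under Study Outcomes, safety events are found through ICD-10-CM billing codes listed in Appendix 5. Under Descriptive Analyses, the plan for them begins "Given the modest sample size and rarity of the safety outcomes" and continues: "we will explore the occurrence of safety outcomes, and present counts and percentages".

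**The concern.** Overall agreement is a poor yardstick for a rare binary outcome. If nearly every patient is event-free, a script can agree with the chart in nearly every record without ever having identified an event. A simple random sample of 10 to 20 charts will usually contain neither a true case nor a flagged record, so it shows neither how many events the script finds (sensitivity) nor how many of its flags are real (PPV).

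This bears on primary objective (ii), the description of safety outcomes in the two groups. The chart check could be met for a transfusion-reaction script that had never met a case, and nothing beside the reported count would show it. Whether a billing code corresponds to the clinical event is a live question here. For example, by its own description in Appendix 5, T80.29XA, one of the two codes for transfusion-transmitted infection, also covers infection after other infusions and injections.

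**Working it through.** The 95% threshold is a chosen criterion, not a derived figure, so there is nothing to reproduce. What can be computed is how the rule behaves.

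**Inputs.** Charts per data point: n = 10 to 20, random (Data Sources). Criterion: 95% overall agreement, read as at least 95% (Data Sources). Event frequency p: not given, only described as rare (Descriptive Analyses), so a range is assumed. For contrast, 28-day mortality is 25%, from the "assumed background survival rate of 0.75 over 28 days" in V. Sample Size.

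**Step 1: what passing means.** For n = 10 to 19, one mismatch gives at most 18/19 = 94.7%, so no mismatch is allowed. For n = 20, 19/20 = 95%, so one is allowed.

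**Step 2: a script that flags nobody.** It disagrees with the chart only in true-event records, so mismatches follow Binomial(n, p). The chance of passing is (1−p)^n for n = 10 to 19, and (1−p)^20 + 20p(1−p)^19 for n = 20.

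At p = 1%:
- n = 10: 0.99^10 = 0.904
- n = 19: 0.99^19 = 0.826
- n = 20: 0.818 + 0.165 = 0.983

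| Assumed p | n = 10 | n = 15 | n = 19 | n = 20 |
|---|---|---|---|---|
| 0.1% | 99.0% | 98.5% | 98.1% | 99.98% |
| 0.5% | 95.1% | 92.8% | 90.9% | 99.6% |
| 1% | 90.4% | 86.0% | 82.6% | 98.3% |
| 2% | 81.7% | 73.9% | 68.1% | 94.0% |
| 3% | 73.7% | 63.3% | 56.1% | 88.0% |
| 5% | 59.9% | 46.3% | 37.7% | 73.6% |
| 10% | 34.9% | 20.6% | 13.5% | 39.2% |
| 25% (mortality) | 5.6% | 1.3% | 0.4% | 2.4% |

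The lowest value in the permitted range is at n = 19 and, up to p = 10%, the highest is at n = 20.

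**Step 3: where it passes more often than not.** The strictest case is n = 19: (1−p)^19 = 0.5 gives p = 1 − 0.5^(1/19) = 3.6%. Below that frequency the script passes more often than not at every permitted n. The corresponding limits are 6.7% for n = 10 and 8.3% for n = 20.

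**Step 4: false flags.** A script that misses every event at p = 1% and wrongly flags another 2% of patients disagrees with the chart in 3% of records. Its pass probabilities are those of the 3% row (56% to 88%), although its PPV is zero.

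**Step 5: would a larger random sample help?** For a 95% chance of at least one event, n must be at least ln(0.05)/ln(1−p): 299 charts at p = 1% and 149 at p = 2%. Enlarging the random sample is not practical, so the way charts are selected has to change.

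**The case against.** Several counter-arguments have weight.

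- **The chart check is not the only safeguard.** The second programmer reviews syntax and logic, and a lookup of listed codes that never returns a TRALI code is the kind of fault that review may catch. This stands, so it would be wrong to infer that scripts are accepted on the charts alone. But that review has no numeric criterion and examines the program, not whether a code reflects what happened to the patient.
- **The problem does not cover the endpoints in general.** A reader might infer that the death script is equally untested. It is not: at 25% mortality a script that flags nobody passes at most 5.6% of the time. The arrhythmia and thromboembolic composites may also be too common for the argument. At 5%, any n from 14 to 19 gives less than a 50% chance of passing (0.95^14 = 0.488).
- **Re-sampling is left open.** A reader might infer that scripts are tuned and judged on the same charts. The protocol neither says so nor rules it out. Silence supports only a request to state it.
- **The consequence is limited.** Safety outcomes are reported as counts and percentages, and no effectiveness estimate depends on them. The protocol also does not say that the counts will be presented as validated.
- **Sampling by script result does not measure sensitivity.** At 1% frequency, ten unflagged charts would all be event-free with probability 0.99^10 = 90%. This is correct and limits what the remedy can claim.

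The argument that such detail belongs in the programming documentation is weaker: the protocol has itself fixed the sample type, its size and the threshold.

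**Conclusion.** The point holds for the six rare transfusion-related outcomes. For these the chart check is close to uninformative: a script that flags nobody passes 83–98% of the time at an assumed 1% frequency and 68–94% at 2%, and more often than not at every permitted sample size below about 3.6%. These figures assume independent random records and an event frequency that the protocol does not give. They describe the chart check alone, not the combined process with the second-programmer review.

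The point does not hold for mortality and may not hold for the two composites. The risk is undetected under-counting or false counting within primary objective (ii), with no effect on the primary effectiveness analysis. The change is worth making because it is cheap.

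**What to change.** Amend Data Sources as follows.

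1. For each safety outcome, replace the simple random sample with one stratified by script result: all flagged records up to 10, plus about 10 unflagged records from plasma recipients.
2. Judge agreement among flagged records (PPV) separately and report it with its exact confidence interval beside each safety count. The interval will be wide: even 10 of 10 confirmed has a two-sided 95% lower limit of 69%.
3. If a script flags nobody, state that it was not tested on a case; do not count it as passed.
4. State that this check does not establish sensitivity for rare events.
5. Base the final match rate on records drawn after the last script change.

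The existing rule can stay for mortality and other common elements, with item 5 added.

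The cost is a wording change in one section, chart review at the upper end of the planned 10–20 per element, and one fresh batch when a script is changed. The gains are a PPV for each outcome with flagged records, open disclosure where there are none, and a final rate that is not drawn from the charts used to correct the script.

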### Exposure

COVID-19 convalescent plasma will be identified with ISBT-128 code (Appendix 1) in local Blood Bank data. First exposure to convalescent plasma is of interest for patients who received multiple doses. Patients can receive convalescent plasma any time during the hospital stay associated with the COVID-19 diagnosis.

### Study Outcomes

- Safety

Safety events related to plasma transfusion were selected from the Centers for Disease Control and Prevention (CDC) National Healthcare Safety Network (NHSN) Biovigilance Component Hemovigilance Module Surveillance Protocol.a The following safety outcomes will be identified by ICD-10-CM billing codes (Appendix 5).

- Transfusion associated circulatory overload (TACO)
- Transfusion-related acute lung injury (TRALI)
- Anaphylactic reaction

---

a The following events were excluded because they are irrelevant for plasma transfusion or because there are no transfusion-specific billing codes. Transfusion-associated graft vs. host disease (TAGVHD) is associated with a cellular product. Delayed hemolytic transfusion reaction (DHTR) and delayed serologic transfusion reaction (DSTR) are associated with red cells containing products. Post transfusion purpura (PTP) is associated with platelets containing products. No transfusion specific billing codes exist for transfusion-associated dyspnea (TAD) allergic reaction and hypotensive transfusion reaction.

- Febrile non-hemolytic transfusion reaction
- Transfusion-transmitted infection
- Acute hemolytic transfusion reaction
- A composite outcome of thrombotic or thromboembolic complication including stroke, myocardial infarction, venous thromboembolism, deep vein thrombosis, and pulmonary embolism
- A composite outcome of cardiac arrhythmias including ventricular tachycardia, ventricular fibrillation, atrial arrhythmia, and cardiac arrest
- Effectiveness
  - Primary:
    - 28-day in-hospital mortality
  - Secondary:
    - Discharge alive
    - ICU transfer
    - Mechanical ventilation

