## II. OBJECTIVES

### A. PRIMARY OBJECTIVES

- (i) To estimate the relative risk of effectiveness outcomes of interest in laboratory confirmed COVID-19 patients who received convalescent plasma compared with COVID-19 patients who did not receive convalescent plasma.
- (ii) To describe safety outcomes of interest in laboratory confirmed COVID-19 patients who received convalescent plasma compared with COVID-19 patients who did not receive convalescent plasma.

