### Cohort Sampling

This is a retrospective cohort study with risk-set sampling for exposure status of convalescent plasma using EHRs in the Baylor Scott & White Health (BSWH) healthcare delivery system. In brief, patients who received convalescent plasma will be matched to a similar population who did not receive convalescent plasma around the same time ( $\pm 2$  days) of transfusion across sites. The administration date of convalescent plasma for the treated population and the matched date for the untreated population are thereafter referred as the index date. The matching scheme for risk-set sampling is defined in step-by-

step points in the following paragraph. The follow-up for the matched cohort will start from the index date and continue until the end of the observation period. The observation period for this study is defined as at least 28 days from the index date. In other words, the index date must be at least 28 days prior to the date of data pull to allow for adequate follow-up and minimize selection bias from informative censoring due to death or discharge for palliative care. An unexposed patient at the index date could receive convalescent plasma during the follow-up and the follow-up will be censored at the administration date of convalescent plasma (Figure 1).

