### **Covariates**

Covariates including those for risk-set sampling and propensity score matching (See Cohort Sampling) will be assessed during baseline and are listed in Appendix 2. Baseline is defined as the period prior to and including the index date. For variables (e.g., vital signs and comedications) assessed at multiple time points, the value closest to the index date will be used. However, for oxygenation, the worst measures 4-12 hours prior to the index date will be used. For variables (e.g., cardiovascular conditions) that are usually collected at hospital admission or possibly in previous healthcare encounters for other health concerns, the value will be searched in the past year from and including the hospital admission date, unless specified otherwise. The lookback period for each covariate is listed in Appendix 2.

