## Appendix 2. Baseline covariates

- Age (continuous)
- Race and ethnicity
- Site
- Comorbidities in the past 12 months including the index date unless specified
  - History of cancer
    - Hematopoietic
    - Solid tumor excluding non-melanoma skin cancer
    - Non-melanoma skin cancer
  - Cardiovascular conditions
    - Stroke
    - Thrombotic or thromboembolic complications including stroke, myocardial infarction, venous thromboembolism, deep vein thrombosis, and pulmonary embolism
    - Hypertension
    - Heart failure
    - Cardiac arrhythmias including ventricular tachycardia, ventricular fibrillation, atrial arrhythmia, and cardiac arrest
  - Chronic respiratory disease
    - Chronic obstructive pulmonary disease
    - Asthma
  - Diabetes
  - Chronic kidney disease 1-4
  - Chronic kidney disease 5 or end-stage renal disease
  - Chronic liver disease
  - History of organ transplantation
  - HIV
  
  - Obesity at admission
  - Sickle cell disease
- Pregnancy status (yes, no) from index date to study completion
- Comedications from hospital admission to the index date
  - Antiviral drugs
    - Remdesivir
    - Lopinavir/Ritonavir
    - Other HIV protease inhibitors.
  - Hydroxychloroquine/Chloroquine
  - Azithromycin
  - Glucocorticoid/Steroids
    - Dexamethasone
    - Prednisone
    - Hydrocortisone
    - Methylprednisolone
  - Anti-platelet agents
  - IL-6 inhibitor/antagonist
    - Tocilizumab
    - Sarilumab

- Siltuximab
  - ACE-Inhibitors (ACEi)/Angiotensin Receptor Blockers (ARBs)
  - Anti-thrombotic drugs
- Disease severity based on level of oxygenation support (Appendix 3) 4-12 hours prior to index
- Vital signs closest to the index date
  - Respiratory rate
  - Heart rate
  - Systolic blood pressure
  - Temperature
- Laboratory results closest to index date
  - Creatinine,
  - D-dimer
  - Cardiac troponin (TnI or TnT)
  - Absolute lymphocyte count
  - Ferritin
  - C-reactive protein

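### The thrombotic and arrhythmia safety composites rest on billing codes, with no stated way to separate new post-index events from conditions already present, so pre-existing conditions can be counted as safety events

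*Protocol*

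**What the plan says.** The second primary objective (Protocol, Section II) is "To describe safety outcomes of interest in laboratory confirmed COVID-19 patients who received convalescent plasma", compared with patients who did not receive it. Study Outcomes sets how the events are found: "The following safety outcomes will be identified by ICD-10-CM billing codes (Appendix 5"). The list includes a thrombotic or thromboembolic composite and a cardiac arrhythmia composite. The analysis is given in Section IV, Descriptive Analyses: "we will explore the occurrence of safety outcomes, and present counts and percentages".

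The statements that bear on timing are these:

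- Cohort Sampling: "The follow-up for the matched cohort will start from the index date and continue until the end of the observation period".
- Covariates: "Baseline is defined as the period prior to and including the index date".
- Exposure: "Patients can receive convalescent plasma any time during the hospital stay associated with the COVID-19 diagnosis".
- Covariates, using cardiovascular conditions as its example: "the value will be searched in the past year from and including the hospital admission date, unless specified otherwise". The section then refers to Appendix 2 for the lookback of each covariate.
- Appendix 2, which lists both composites as baseline conditions: "Comorbidities in the past 12 months including the index date unless specified".

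Appendix 5 holds the outcome codes. Appendix 4, meant to hold the time points of the data elements, is an empty table to be completed during programming.

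**The concern.** A safety event attributed to plasma has to begin after plasma, or after the matched date in an unexposed patient. The two composites are made of conditions that hospitalised COVID-19 patients may already have on arrival or may develop before transfusion. The protocol recognises this by listing the same composites as baseline covariates, yet it gives no rule for telling a baseline case from an outcome case.

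Two distortions are possible. If pre-index conditions are equally common in both groups, they inflate both percentages and pull the ratio towards one, which can hide a difference. If they are unequally common, for instance because clinicians weigh an earlier clot or arrhythmia when deciding on plasma, they can create a difference or reverse one. The transfusion-specific outcomes, such as circulatory overload or acute lung injury from transfusion, are little affected, because their codes refer to the transfusion itself.

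**Working it through.** No figure in the protocol depends on this point, so there is none to reproduce. The check is a comparison of sections, followed by an illustration.

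**Comparison of the text**

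1. *Outcome window.* Neither Study Outcomes nor Descriptive Analyses gives a window, an onset condition or a prior-event exclusion for safety. By contrast, the sentence on deaths in Descriptive Analyses names 7, 14, 21 and 28 days after the index date.
2. *Hospital time before the index date.* Plasma may be given at any point in the stay. Secondary Analyses plans strata of under 72 hours and at least 72 hours from admission to index, so three or more inpatient days before time zero are expected for some patients.
3. *Same condition on both sides.* The thrombotic composite has the same components in Study Outcomes and Appendix 2, and so does the arrhythmia composite.
4. *Index day.* Baseline includes the index date and follow-up starts on it. An event on that day can be both covariate and outcome. This needs no assumption about billing data.
5. *Lookback.* Take an embolism on hospital day 2 with plasma on day 4. Under the sentence in Covariates the search stops at admission, so the event is not baseline. Under Appendix 2 the search runs to the index date, so it is. Neither text says whether the event's code also counts as an outcome.
6. *Code content.* Appendix 5 counts chronic atrial fibrillation (I48.2) under arrhythmia and precerebral artery stenosis without infarction (I65.xx) under stroke. Both can long precede the index date.

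**Illustration (all rates assumed; the documents give none)**

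Let q be the share of patients with a pre-index code that is counted, and p the true post-index risk. Then observed risk = q + (1 − q) × p, and the pre-index share of counted patients = q / observed risk.

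Equal q in both groups, with p = 6% exposed and 4% unexposed (true ratio 1.50):

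- q = 5%: 0.05 + 0.95 × 0.06 = 10.7%; 0.05 + 0.95 × 0.04 = 8.8%; ratio 1.22; pre-index share in the exposed 0.05 / 0.107 = 47%.
- q = 10%: 0.10 + 0.90 × 0.06 = 15.4%; 0.10 + 0.90 × 0.04 = 13.6%; ratio 1.13; share 65%.
- q = 20%: 0.20 + 0.80 × 0.06 = 24.8%; 0.20 + 0.80 × 0.04 = 23.2%; ratio 1.07; share 81%.

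Unequal q, with no true effect (p = 4% in both groups):

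- q = 10% exposed, 5% unexposed: 0.10 + 0.90 × 0.04 = 13.6%; 0.05 + 0.95 × 0.04 = 8.8%; ratio 1.55.
- q = 5% exposed, 10% unexposed: 8.8% and 13.6%; ratio 0.65.

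**The case against.** A reader might infer that the protocol has no timing rule and that events before plasma are counted. The documents do not support that. Cohort Sampling starts follow-up at the index date, which implies post-index ascertainment, and no section says that earlier events count. What is missing is the step that applies this rule to a billing code.

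Other points on the sponsor's side:

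- *Dating of codes.* That billing codes cannot be dated within a stay is an outside assumption. Data Sources promises time points for the extracted elements and validation against chart review, and Appendix 2's lookback presupposes that conditions can be placed relative to the index date. A separate analysis plan may add the rule. This softens the gap but does not close it: Appendix 4 is empty, Section IV is itself titled a statistical analysis plan and addresses safety, and the index-day overlap would remain.
- *Lookback.* A reader might infer that the two lookbacks by themselves turn pre-plasma events into outcomes. They do not. They decide what is recorded as baseline. The Covariates sentence allows for exceptions and the section points to Appendix 2, which can be read as governing and agrees with the general definition of baseline. The wording still needs aligning.
- *Balance.* The conditions are candidate propensity-score covariates, and groups are matched on days from admission to index. Both should reduce pre-index imbalance in a matched comparison. However, Descriptive Analyses does not say that the safety counts use the matched cohort, and balance would not remove the dilution seen with equal q.
- *Descriptive purpose.* No safety effect estimate or test is planned. This stands and lowers the severity, although the counts still answer a primary objective that compares the groups.

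**Conclusion.** The concern holds in a limited form. Followed as written, the plan lets conditions present before the index time enter the thrombotic and arrhythmia counts for primary objective (ii), because it does not say how a code is placed after the index time or how prevalent cases are handled. The index-day overlap, the chronic codes and the differing lookback end points are in the text. How often undated codes would cause misclassification is not, and rests on how the codes are dated in the extracted data.

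The size is therefore unknown. The illustrative ratios (1.50 falling to between 1.22 and 1.07; no effect appearing as 1.55 or 0.65) show direction and possible scale under assumed rates and are not estimates for this study. The point should be fixed before the safety data are analysed. It does not rank as critical, since the safety analysis is descriptive and mortality and the other effectiveness outcomes are unaffected.

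**What to change.** For the two composites, amend Study Outcomes and Descriptive Analyses as follows:

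- Count only new events dated after the index time and within 28 days of it, using dated EHR diagnosis, imaging or procedure records. Use a present-on-admission indicator as support where available, not as a required condition.
- Report patients with the same condition before the index time separately, or remove them from that composite's denominator. A code for a long-standing condition then cannot make an event by itself.
- List events of uncertain timing separately.

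Align Covariates and Appendix 2 to one lookback that ends just before the index time, so that no event is both covariate and outcome.

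The cost is protocol wording and a few more extracted fields. The plan already links plasma orders to an administration date and time, and already foresees chart-review validation. The drawback is smaller counts and some events whose timing stays unclear.
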